10.1.7 Relationship to Study Procedures

Relationship (causality) to study procedures should be determined for all PTEs and AEs.

The relationship should be assessed as Related if the investigator considers that there is reasonable possibility that an event is due to a study procedure. Otherwise, the relationship should be assessed as Not Related.

10.1.8 Start Date

The start date of the AE/PTE is the date that the first signs/symptoms were noted by the subject and/or investigator.

10.1.9 Stop Date

The stop date of the AE/PTE is the date at which the subject recovered, the event resolved but with sequelae or the subject died.

10.1.10 Frequency

Episodic AEs/PTE (eg, vomiting) or those which occur repeatedly over a period of consecutive days are intermittent. All other events are continuous.

10.1.11 Action Concerning Study Drug

- Drug withdrawn – a study drug is stopped due to the particular AE.
- Dose not changed – the particular AE did not require stopping a study drug.
- Unknown – only to be used if it has not been possible to determine what action has been taken.
- Not Applicable – a study drug was stopped for a reason other than the particular AE eg, the study has been terminated, the subject died, dosing with study drug was already stopped before the onset of the AE.
- Dose Interrupted – the dose was interrupted due to the particular AE.

10.1.12 Outcome

- Recovered/Resolved – Subject returned to first assessment status with respect to the AE/PTE.
- Recovering/Resolving – the intensity is lowered by 1 or more stages: the diagnosis or signs/symptoms has almost disappeared; the abnormal laboratory value improved, but has not returned to the normal range or to Baseline; the subject died from a cause other than the particular AE/PTE with the condition remaining “recovering/resolving”.
- Not recovered/not resolved – there is no change in the diagnosis, signs or symptoms; the intensity of the diagnosis, signs/ symptoms or laboratory value on the last day of the observed study period has got worse than when it started; is an irreversible congenital anomaly; the subject died from another cause with the particular AE/PTE state remaining “Not recovered/not resolved”.

- Resolved with sequelae – the subject recovered from an acute AE/PTE but was left with permanent/significant impairment (eg, recovered from a cardiovascular accident but with some persisting paresis).
- Fatal – the AEs/PTEs which are considered as the cause of death.
- Unknown – the course of the AE/PTE cannot be followed up due to hospital change or residence change at the end of the subject’s participation in the study.

10.2 Procedures

10.2.1 Collection and Reporting of AEs

10.2.1.1 PTE and AE Collection Period

Collection of PTEs will commence from the time the subject signs the informed consent to participate in the study and continue until the subject is first administered study drug on Day 1 for Part 1, or Pre-enrollment Enrichment Visit for Part 2, or until screen failure. For subjects who discontinue prior to study drug administration, PTEs are collected until the subject discontinues study participation.

Collection of AEs will commence from the time that the subject is first administered study drug (Day 1 of Period 1). Routine collection of AEs will continue until the Follow-up Visit/Call or Early Termination.

10.2.1.2 PTE and AE Reporting

At each study visit, the investigator will assess whether any subjective AEs have occurred. A neutral question, such as “How have you been feeling since your last visit?” may be asked. Subjects may report AEs occurring at any other time during the study. Subjects experiencing a serious PTE must be monitored until the symptoms subside and any clinically relevant changes in laboratory values have returned to Baseline or there is a satisfactory explanation for the change. Non-serious PTEs, related or unrelated to the study procedure, need not to be followed-up for the purposes of the protocol.

All subjects experiencing AEs, whether considered associated with the use of the study drug or not, must be monitored until the symptoms subside and any clinically relevant changes in laboratory values have returned to Baseline or until there is a satisfactory explanation for the changes observed. All PTEs and AEs will be documented in the PTE/AE page of the eCRF, whether or not the investigator concludes that the event is related to the drug treatment. The following information will be documented for each event:

1. Event term.
2. Start and stop date and time.
3. Frequency.
4. Intensity.

5. Investigator's opinion of the causal relationship between the event and administration of study drug(s) (related or not related) (not completed for PTEs).
6. Investigator's opinion of the causal relationship to study procedure(s), including the details of the suspected procedure.
7. Action concerning study drug (not applicable for PTEs).
8. Outcome of event.
9. Seriousness.

10.2.2 Collection and Reporting of SAEs

When an SAE occurs through the AE collection period it should be reported according to the following procedure:

A Takeda SAE form must be completed, in English, and signed by the investigator immediately or within 24 hours of first onset or notification of the event. The information should be completed as fully as possible but contain, at a minimum:

- A short description of the event and the reason why the event is categorized as serious.
- Subject identification number.
- Investigator's name.
- Name of the study drug(s).
- Causality assessment.

The SAE form should be transmitted within 24 hours to the attention of the contact listed in Section 1.0.

Any SAE spontaneously reported to the investigator following the AE collection period should be reported to the sponsor if considered related to study participation.

Reporting of Serious PTEs will follow the procedure described for SAEs.

10.2.3 Reporting of Abnormal Liver Function Tests

If a subject is noted to have ALT or AST elevated $>3 \times$ ULN on 2 consecutive occasions, the abnormality should be recorded as an AE. In addition, an LFT Increases eCRF must be completed providing additional information on relevant recent history, risk factors, clinical signs and symptoms and results of any additional diagnostic tests performed.

If a subject is noted to have ALT or AST $>3 \times$ ULN and total bilirubin $>2 \times$ ULN for which an alternative etiology has not been identified, the event should be recorded as an SAE and reported as per Section 10.2.2. The investigator must contact the Medical Monitor for discussion of the relevant subject details and possible alternative etiologies, such as acute viral hepatitis A or B or other acute liver disease or medical history/concurrent medical conditions. Follow-up laboratory

tests as described in Section 9.1.8 must also be performed. In addition, an LFT Increases eCRF must be completed and transmitted with the Takeda SAE form (as per Section 10.2.2).

10.3 Follow-up of SAEs

If information is not available at the time of the first report becomes available at a later date, the investigator should complete a follow-up SAE form or provide other written documentation and fax it immediately within 24 hours of receipt. If the subject was hospitalized, copies of any relevant data from the hospital records (eg, ECGs, laboratory tests, discharge summary, postmortem results) should be sent to the addressee, if requested.

All SAEs should be followed up until resolution or permanent outcome of the event. The timelines and procedure for follow-up reports are the same as those for the initial report.

10.3.1 Safety Reporting to Investigators, IRBs, and Regulatory Authorities

The sponsor will be responsible for reporting all suspected unexpected serious adverse reactions (SUSARs) and any other applicable SAEs to regulatory authorities, investigators, and IRBs as applicable, in accordance with national regulations in the countries where the study is conducted. Relative to the first awareness of the event by/or further provision to the sponsor or sponsor's designee, SUSARs will be submitted to the regulatory authorities as expedited report within 7 days for fatal and life-threatening events and 15 days for other serious events, unless otherwise required by national regulations. The sponsor will also prepare an expedited report for other safety issues where these might materially alter the current benefit-risk assessment of the study drug/sponsor supplied drug or that would be sufficient to consider changes in the study drug/sponsor supplied drug administration or in the overall conduct of the trial. The study site also will forward a copy of all expedited reports to his or her IRB in accordance with local regulations.

11.0 STUDY-SPECIFIC COMMITTEES

No steering committee, data safety monitoring committee, or clinical endpoint committee will be used in this study.

12.0 DATA HANDLING AND RECORDKEEPING

The full details of procedures for data handling will be documented in the Data Management Plan. AEs, PTEs, medical history, and concurrent medical conditions will be coded using the Medical Dictionary for Regulatory Activities (MedDRA). Drugs will be coded using the World Health Organization Drug Dictionary (WHODRUG).

12.1 eCRFs

Completed eCRFs are required for each subject who signs an informed consent.

The sponsor or its designee will supply study sites with access to eCRFs. The sponsor will make arrangements to train appropriate site staff in the use of the eCRF. These forms are used to transmit the information collected in the performance of this study to the sponsor and regulatory authorities. eCRFs must be completed in English.

After completion of the entry process, computer logic checks will be run to identify items, such as inconsistent dates, missing data, and questionable values. Queries may be issued by Takeda personnel (or designees) and will be answered by the site.

The principal investigator must review the eCRFs for completeness and accuracy and must e-sign the appropriate eCRFs as indicated. Furthermore, the investigator must retain full responsibility for the accuracy and authenticity of all data entered on the eCRFs.

After the lock of the study database, any change of, modification of or addition to the data on the eCRFs should be made by the investigator with use of change and modification records of the eCRFs. The principal investigator must review the data change for completeness and accuracy, and must sign, or sign and date.

The eCRFs will be reviewed for completeness and acceptability at the study site during periodic visits by the sponsor or its designee. The sponsor or its designee will be permitted to review the subject's medical and hospital records pertinent to the study to ensure accuracy of the eCRFs. The completed eCRFs are the sole property of the sponsor and should not be made available in any form to third parties, except for authorized representatives of appropriate governmental health or regulatory authorities, without written permission of the sponsor.

12.2 Record Retention

The investigator agrees to keep the records stipulated in Section 12.1 and those documents that include (but are not limited to) the study-specific documents, the identification log of all participating subjects, medical records, temporary media such as thermal sensitive paper, source worksheets, all original signed and dated informed consent forms, subject authorization forms regarding the use of personal health information (if separate from the informed consent forms), electronic copy of eCRFs, including the audit trail, and detailed records of drug disposition to enable evaluations or audits from regulatory authorities, the sponsor or its designees. Any source documentation printed on degradable thermal sensitive paper should be photocopied by the site and filed with the original in the subject's chart to ensure long-term legibility. Furthermore, International Conference on Harmonisation (ICH) E6 Section 4.9.5 requires the investigator to

retain essential documents specified in ICH E6 (Section 8) until at least 2 years after the last approval of a marketing application for a specified drug indication being investigated or, if an application is not approved, until at least 2 years after the investigation is discontinued and regulatory authorities are notified. In addition, ICH E6 Section 4.9.5 states that the study records should be retained until an amount of time specified by applicable regulatory requirements or for a time specified in the study site agreement between the investigator and sponsor.

Refer to the study site agreement for the sponsor's requirements on record retention. The investigator should contact and receive written approval from the sponsor before disposing of any such documents.

13.0 STATISTICAL METHODS

13.1 Statistical and Analytical Plans

A statistical analysis plan (SAP) will be prepared and finalized prior to database lock. This document will provide further details regarding the definition of analysis variables and analysis methodology to address all study objectives.

13.1.1 Analysis Sets

13.1.1.1 Safety Set

The Safety Analysis Set will consist of all subjects who are enrolled and received 1 dose of study drug. Subjects in this analysis set will be used for demographics, Baseline characteristics, and safety summaries.

13.1.1.2 PK Set

The PK Set will consist of all subjects who receive study drug and have at least 1 measurable plasma concentration or amount of drug in the urine.

If any subjects are found to be noncompliant in dosing schedule or with incomplete data, a decision will be made on a case-by-case basis as to their inclusion in the analysis, but the data will be presented in the subject listings.

13.1.1.3 PD Set

The PD Set will consist of all subjects who receive study drug and have at least 1 postdose PD measurement.

If any subjects are found to be noncompliant in dosing schedule or with incomplete data, a decision will be made on a case-by-case basis as to their inclusion in the analysis but will be presented in the subject listings.

13.1.2 Analysis of Demographics and Other Baseline Characteristics

Demographic and Baseline characteristics will be summarized for all randomized subjects. For continuous variables (eg, age, height, weight, and BMI), the summary will consist of descriptive statistics (number of subjects, mean, SD, minimum, median, and maximum). For categorical variables (eg, ethnicity and race), the summary will consist of number and percentage of subjects in each category.

13.1.3 PK Analysis

Plasma concentrations of TAK-071, donepezil, and scopolamine will be summarized from each treatment using descriptive statistics.

Individual plasma concentration data versus time will be presented in a data listing.

Plasma PK parameters for TAK-071, donepezil, and scopolamine will be summarized separately.

A more detailed analysis will be presented in the SAP. The relationship between PK and PD may be explored and detailed in a separate plan. Additional analyses may also be considered.

13.1.4 PD Analysis

13.1.4.1 Cognitive Testing Analysis

To address the statistical hypotheses related to the time course of scopolamine effects, cognitive endpoints will be analyzed using a mixed analysis of variance (ANOVA) model appropriate for a 5-period crossover with fixed factors for period, sequence, treatment, hour, and treatment by hour. Additionally, the model will contain a random factor subject nested in sequence (the between-subject error) and a random residual error term (the within-subject error). A 2-sided t-test ($\alpha=0.05$) using the within subject mean squared error from the mixed ANOVA model will be examined to test the primary hypothesis. Treatment differences, 2-sided 95% CIs, 2-sided p-values, and effect sizes will be presented for all time points, with 2 hours post scopolamine being the time frame for the primary endpoint.

To address the statistical hypotheses related to area under the effect curve (AUEC) endpoints, cognitive endpoints will be analyzed using an ANOVA model appropriate for a 5-period crossover with fixed factors for treatment, period, and sequence. Additionally, the model will contain a random factor subject nested in sequence (the between-subject error) and a random residual error term (the within-subject error). A 2-sided t test ($\alpha=0.05$) using the within subject mean squared error from the mixed ANOVA model will be examined to test the statistical hypothesis.

For AUEC endpoints, the natural log scale treatment differences (eg, the primary treatment comparison of Treatment Y – Treatment X) will be exponentiated and reported as a mean percent change along with 95% CIs for the true mean percent change as a summary measure. Other statistical treatments (such as multivariate analysis of covariance [ANCOVA]) will be outlined in the SAP.

The Baseline cognitive measure will be included in the model as a covariate.

Other statistical analyses will be performed as appropriate.

13.1.4.2

CCI

CCI

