The SC administration of scopolamine has a $t_{1/2z}$ of 3 to 4 hours and reaches C_{max} within 10 to 30 minutes. The cognitive impairment induced by SC administration of scopolamine appears to be maximal approximately 1 to 2 hours after administration and disappears after 6 to 8 hours postinjection, allowing for a minimal but sufficient period of subject supervision before subjects are discharged safely on Day 3. The minimum 21-day washout between the last dose in a period and the first dose in the subsequent period will be sufficient to ensure no drug carryover effect.

TAK-071 and donepezil will be administered 24 and 3 hours, respectively, prior to administration of scopolamine so that the t_{max} of TAK-071 (26 hours in plasma after an 80 mg dose) and donepezil (approximately 3 to 4 hours in plasma) occur at approximately the same time as the maximal scopolamine-induced cognitive impairment effects (approximately 1 to 2 hours after SC administration). The time of administration of TAK-071 relative to scopolamine may be adjusted upon review of emerging PK data from the FIH study.

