13.3 Determination of Sample Size

For Part 1, a sample size of 6 enrolled and 4 completers is considered sufficient for providing guidance on the TAK-071 dose selection for Part 2, the main study. This is not based on any statistical power.

For Part 2, a sample size of 26 subjects, approximately 3 subjects for each of the 10 sequences of the 5-period cross-over, will be used and is considered sufficient for evaluation of the primary cognitive endpoints for this study based on consideration of published scopolamine model literature and expert advice. Subjects who drop-out will not be replaced, therefore to ensure there are enough completers a total of 40 subjects will be recruited (4 per sequence).

In particular, this sample-size calculation was based on a consideration of effect sizes seen in a similar study [21]. Using a 2-sided alpha level of 0.05, this study has a 90% power to detect an effect size of 0.67 in the GMLT (sum of 5 trials) total number of errors for the primary treatment comparison of TAK-071+scopolamine vs placebo+scopolamine, assuming a total of 26 subjects complete the study and provide primary endpoint data.

At least 26 subjects will complete the study if 40 subjects are randomized, assuming the drop-out rate does not exceed 33%.

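### Does testing the 2-hour GMLT comparison against one residual variance, pooled over all hours and all five treatments, call for a change to the plan?

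*Protocol*

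**What the plan says.** Protocol section 13.1.4.1, repeated in the Study Summary, analyses the cognitive endpoints over time with fixed period, sequence, treatment, hour and treatment-by-hour, and Baseline as a covariate. The random part is "a random factor subject nested in sequence (the between-subject error) and a random residual error term (the within-subject error"). The primary hypothesis is tested by a 2-sided t-test at 0.05 "using the within subject mean squared error from the mixed ANOVA model will be examined to test the primary hypothesis", with 2 hours after scopolamine as the primary time.

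Three other places bear on that error term:

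- Protocol Appendix A (Part 2) schedules the cognitive battery at 1, 2, 3, 4, 6, 8 and 10 hours, so seven postdose results per period enter the model.
- Protocol section 6.3.2 says the impairment "appears to be maximal approximately 1 to 2 hours after administration and disappears after 6 to 8 hours postinjection".
- Protocol Table 6.a includes Treatment A, which contains no scopolamine.

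The SAP was written after enrolment had been paused and then not resumed. Its section 5.1 says the primary endpoint no longer applies, section 7.9 marks the efficacy analysis as not applicable, and section 7.10.3 says the pharmacodynamic parameters will be neither listed nor summarised. Section 7.1 records that 12 subjects were enrolled in Part 2 and that none started Period 2.

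**The concern.** A single residual variance is the right yardstick for the 2-hour contrast only if within-subject variability is about the same at every hour and in every arm. The protocol does not state this, and its own description makes it doubtful. The endpoint is a count of errors, the drug effect peaks at the primary time and has gone by the late tests, and one arm in five never receives scopolamine. If the response to scopolamine varies from occasion to occasion, the spread at 2 hours in the scopolamine arms exceeds the average spread, the standard error is too small and the test rejects too often.

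The error can also run the other way. Stable differences between subjects in scopolamine response cancel in the difference between Treatments C and B. The model has only a subject intercept, so those differences fall into the residual, inflate the standard error and cost power.

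There is also no subject-by-period term, so tests within one period are treated as independent given the subject. At stake are the type I error and interval coverage of the one confirmatory comparison.

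**Working it through.** **The plan's own figure.** Section 13.3 states: "Using a 2-sided alpha level of 0.05, this study has a 90% power to detect an effect size of 0.67 in the GMLT", "assuming a total of 26 subjects complete the study and provide primary endpoint data". Reading 0.67 as mean difference over the SD of the paired difference:

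- Noncentrality = 0.67 × √26 = 3.42. Power is 0.907 on 25 df and 0.922 on 96 df, so the stated 90% is reproduced.
- If 0.67 were scaled by the residual SD, noncentrality = 0.67 × √(26/2) = 2.42 and power is only 0.64 to 0.67. The protocol does not name the scale; the paired reading is the one that reproduces its figure.
- Dropout: 26/(1 − 0.33) = 38.8, so 39; and 40 × 0.67 = 26.8. Both agree with 40 randomised.

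**Degrees of freedom at 26 completers.**

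- Planned model: 26 × 5 × 7 = 910 results, less 26 subject, 4 period and 34 treatment-by-hour parameters, leaves 846 df.
- 2-hour data only, all arms: 130 − 26 − 4 − 4 = 96 df.
- 2-hour data, arms B to E: 104 − 26 − 4 − 3 = 71 df.
- The critical value moves from 1.963 (846 df) to 1.994 (71 df), about 0.03. The df count itself is a minor matter.

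**How the level moves.** With many df, actual level ≈ 2 × [1 − Φ(1.96 × k)], where k is the model's standard error divided by the true one. For example, a model standard error of 0.37 against a true 0.49 gives k = 0.755, 1.96 × 0.755 = 1.48 and a level of 13.9%. Simulation of that case gave 14.0%.

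**Simulation with no difference between C and B.** All used the Table 6.a sequences and seven hours. Every variance below is an assumption, because the documents give no SD or correlation.

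Unequal SDs, 26 completers, 6000 runs per scenario, Baseline covariate not included:

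| Assumption | Actual level of the nominal 5% test |
|---|---|
| Equal SDs, no within-period correlation | 5.3% |
| Equal SDs, within-period correlation 0.3 / 0.6 | 6.0% / 6.6% |
| Scopolamine-arm SD 1.5 times placebo at all hours | 6.1–8.3% |
| Scopolamine-arm SD ratio 1.25 at peak, decaying to placebo level by 8 h | 9.1–10.6% |
| Same, ratio 1.5 | 10.7–13.3% |
| Same, ratio 2 | 15.2–16.5% |
| 2-hour SD lower than at other hours by 1.25 times | 1.7–2.8% |
| Same, by 1.5 times | 0.5–0.9% |

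Random scopolamine response, residual variance 1, subject-by-period variance 0.5, 4000 runs per scenario:

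| Response variance at peak | Completers | Actual level |
|---|---|---|
| None | 30 | 6.1% |
| Occasion-level 0.1 / 0.25 / 0.5 | 26 and 30 | 6.4% / 6.9–7.6% / 8.2–8.3% |
| Occasion-level 1 / 2 / 3 | 30 | 11.4% / 14.0% / 15.0% |
| Occasion-level 0.25–0.5 with subject-level 0.5–3 | 26 and 30 | 4.5–7.4% |
| Occasion-level 2 with subject-level 2 | 30 | 9.8% |
| Subject-level only, 2 / 4 | 30 | 2.9% / 2.3% |

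Adding the Baseline covariate at 26 completers gave 11.2% and 13.8% for occasion-level variance 1 and 2, 5.7–7.6% for modest mixed variance and 2.1% for purely subject-level variance. The covariate does not alter the picture.

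**Comparators.** A 2-hour crossover analysis restricted to arms B to E held 4.3–5.6% in the random-response scenarios. In the unequal-SD scenarios a paired t-test on C minus B held 4.4–5.8%, and a 2-hour analysis keeping Treatment A ran at 4.4–7.8%.

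**Can the contrast be formed?** C minus B within a subject needs at least two periods from that subject. SAP section 7.1 says no one began Period 2, so no subject contributes both treatments. Twelve subjects over five treatments is on average 12/5 = 2.4 per treatment, in one period only.

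**The case for a change.** The strongest case for acting is that the primary error term is expressly fixed in the protocol, so the clauses leaving further methodology to the SAP do not cure it. Equal variance is hard to believe given the protocol's own time course. Separate simulations agree that the level can roughly double or triple, and the results at 40 subjects are similar, so a larger trial would not help. The remedy is also cheap. The same section already uses a crossover model with one value per period for the area-under-effect endpoints, and the 90% power reproduces as a paired comparison, which is what a 2-hour analysis would deliver. The study was meant to support phase 2 work, so the rule might be reused.

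Most of this stands as a description of the rule. Three things limit it:

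- Size and direction rest wholly on assumed variances. Modest or mixed variability leaves the level near 5 to 8%, and some settings make the test conservative.
- The only text on variability, in protocol section 6.3.3.3, expects subcutaneous dosing to give a more reproducible profile, and section 7.3 screens on the 2-hour response. Neither shows equal variance, but both lean against very large occasion-to-occasion variation.
- The missing subject-by-period term adds only about one percentage point; unequal variance is the driver.

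Possible reuse elsewhere does not justify changing a trial that will not run this analysis.

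**Conclusion.** No change is needed, because there is no gain to be had. The protocol's 2-hour test keeps its 5% level and 95% coverage only if within-subject variance is about equal across hours and treatments, which the protocol neither states nor supports. Under the assumed variances, the level runs from about 2% to 15% when the scopolamine response varies at random, and from 0.5% to 16.5% when SDs differ by hour and arm. The documents do not allow that range to be narrowed.

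The SAP has withdrawn the primary endpoint and all pharmacodynamic analysis, and the data cannot supply a within-subject C minus B difference. A different error term would alter nothing the trial reports or concludes. The point is a conditional comment on a superseded protocol rule. It would matter only if the pharmacodynamic analysis were revived, in which case a 2-hour crossover analysis of arms B to E would hold its level at a cost of about 0.03 in the critical value.
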